7.2.3 Safety Assessments

7.2.3.1 Adverse Events

Adverse events will be coded according to the MedDRA version 23.1.

(1) Treatment Emergent Adverse Events/ Treatment Emergent Serious Adverse Events (TEAEs/TESAEs)

AEs will be classified as ‘treatment-emergent’ if they arise following the first administration of study medication in the treatment period (after randomization) or if a pre-dose AE increases in severity following dosing in the treatment period (after randomization).

Rule to determine TEAE using onset date of AEs:

An AE is classified as treatment emergent if it newly occurred on or after the first dose of study drug. According to this data handling, for the severity part in the above TEAE definition, the AE with upgraded severity and with the new onset date during the treatment period will be automatically included as TEAE.

(2) Adverse Event Related to Study Drug

A TEAE is considered “adverse event related to study drug” if it has been assessed as having a “reasonable possibility” in relationship to the study drug.

(3) Duration of Adverse Events

Duration of Adverse Events (days) = AE stop date – AE start date + 1.

(4) Time to AE onset

For DBT period, time to AE onset (days) = AE start date – the first treatment date in DBT period + 1.

For DBE period, time to AE onset (days) = AE start date – the first treatment date in DBE period + 1.

7.2.3.2 Physical examination

If “Abnormal, Unchanged from previous assessment” is selected and there is no available data of “Clinically Significant” or “Not Clinically Significant” in the previous assessment, the analysis value will be regarded as “Abnormal, Clinically Significant”.

7.2.3.3 Laboratory Tests

(1) Criteria for pre-defined limit

Liver function:

- ALT $\geq 10 \times \text{ULN}$
- $8 \times \text{ULN} \leq \text{ALT} < 10 \times \text{ULN}$
- $5 \times \text{ULN} \leq \text{ALT} < 8 \times \text{ULN}$
- $3 \times \text{ULN} \leq \text{ALT} < 5 \times \text{ULN}$
- $1 \times \text{ULN} \leq \text{ALT} < 3 \times \text{ULN}$

The above same criteria will be applied to AST.

- Total Bilirubin $\geq 2 \times \text{ULN}$
- $1 \times \text{ULN} \leq \text{Total Bilirubin} < 2 \times \text{ULN}$

7.2.3.4 12-Lead ECG

(1) Criteria for pre-defined limit

12-lead ECG:

- Baseline QTc $< 450 \text{ msec}$ and $> 500 \text{ msec}$ at any post baseline
- Baseline QTc $< 450 \text{ msec}$ and $500 \text{ msec} \geq \text{QTc} > 480 \text{ msec}$ at any post baseline
- Baseline QTc $< 450 \text{ msec}$ and $480 \text{ msec} \geq \text{QTc} > 450 \text{ msec}$ at any post baseline
- Increase from baseline in QTc $> 30 \text{ msec}$, 60msec at any post baseline

The above same criteria will be applied to QTcF and QTcB.

7.2.4 Data Handling of PK data and melanin density data

The PK data and melanin density (MD) data handling will be confirmed during blinded data review (BDR). PK data and MD data that are considered "invalid" will be flagged in the listing and will be excluded from the calculation of summary statistics. Due to the nature of PK data and MD data, some issues may only be discovered after PK data and MD data are unblinded. Should new issues be identified post unblinding, and new data handling rules would have to be applied, a separate PK data and MD data handling document will be produced to provide detailed rationale and decision making. If there is clear evidence that PK sample handling errors, MD handling errors, or other factors are identified after data unblinding and these errors have led to unexpected erroneous data, then these erroneous data will be regarded as "invalid", full explanations will be given in the PK data and MD data handling document.

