11.6 Maintenance of the Study Blind and Unblinding

All study treatments will be double-blinded during the 52-week study; neither the subject nor the study site personnel will know which treatment is being taken. Each subject's treatment will be given a unique code number, traceable to the identity, dose, and batch number of the study medication. The IWRS will be used to hold treatment codes for each subject. The codes will only be accessible to authorized unblinded IWRS users.

The IWRS should not normally be accessed with a request to break the treatment code for reasons other than safety or in an emergency. Should the Investigator wish to break the code for such reasons, he/she are advised to consult the Sponsor (or designee) in advance where feasible. If this is not possible, the Investigator may access the IWRS to obtain the treatment code and provide the system with the reason for breaking the blind. The Sponsor should be notified as soon as possible thereafter. If the blind is broken for any individual subject, the subject must be withdrawn from the study, and any procedures accompanying withdrawal will be performed (Section 8.5).

The Sponsor and study team will remain blinded throughout the duration of the double-blind treatment of the study.

Because PK analysis will only be performed on samples from subjects receiving active medication, unblinded randomization codes will be given to PK lab.

An electronic list of randomization codes will be retrieved from IWRS and transferred to the Sponsor at the end of the study.

Since melanin density values could potentially be unblinding, adequate measures will be taken to protect the spectrophotometry data from disclosure to the sponsor and the study team until the end of the study. Melanin density component data will be measured by the dedicated unblinded site staff, securely uploaded to and processed by the dedicated unblinded data management team. The data handling procedure for melanin density will be described in the data management plan.

The handling of data that could potentially unblind the study will be defined in relevant study procedures documents (e.g., Unblinded Data Management plan or equivalent).

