H10: There is no treatment difference between MT-7117 [REDACTED] and placebo in the percentage of subjects who are responders at Week 26 based on average daily sunlight exposure time to first prodromal symptoms using the within-subject meaningful change of 66 minutes increase.

H11: There is no treatment difference between MT-7117 [REDACTED] and placebo in change from

baseline for total score in the domain of physical function in the PROMIS-57 at Week 26.

H12: There is no treatment difference between MT-7117 [REDACTED] and placebo in change from baseline for total score in the domain of physical function in the PROMIS-57 at Week 26.

Subgroup Analysis

The consistency of treatment effect on the primary endpoint across different subgroups will be explored based on the ITT1 population and the primary estimand for the following subgroups using the primary efficacy analysis.

- Gender (Male, Female)
- Age group (age <18, 18=< age)
[REDACTED]
- Ethnicity (Hispanic or Latino, Non-Hispanic or Latino, Others)
- Race (White, Black or African American, Asian(Japanese), Others)
- BMI (BMI <30, BMI \geq 30 kg/m²)
[REDACTED]
[REDACTED]
- Seasonality1 (Randomized in Spring and Summer inclusive, Other)
- Seasonality2 (Week 26 visit in Spring and Summer inclusive, Other)
- Average melanin density at BL (>=Median, <Median)
- Fitzpatrick scale test category (I-II or III-VI)
- Protoporphyrin (>=Median, <Median)
- Porphyrin (>=Median, <Median)
- EPP vs XLP
[REDACTED]
[REDACTED]
[REDACTED]
[REDACTED]
[REDACTED]
- Study Drug Compliance by Week 26 (no study drug suspension, any suspension or permanent study drug discontinuation)

Bayesian analysis for adult and adolescent subgroups

Age group (age <18, 18=<age)

In order to estimate treatment effects for adult and adolescent for the primary endpoint, Bayesian subgroup hierarchical model and Commensurate prior model will be performed using both adolescent and adult subgroup data in order to get greater precision on treatment effect

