The following endpoint will be listed and summarized by treatment and planned time point using descriptive statistics. The value of melanin density, change from baseline and % change from baseline in melanin density at each visit by skin segments and average of 6 skin segments will be plotted by treatment. The average of 6 skin segments for the melanin density and for the change from baseline in melanin density at each visit, will be analysed using MMRM model similar to the analyses for the primary endpoint. A subgroup analysis by region (North America, Europe, Japan, Australia), by Fitzpatrick scale test category (I-II or III-VI), by Melanin density at BL (\geq Median, $<$ Median) and by the [REDACTED] will be done.

- Change from baseline and % change from baseline in melanin density at each visit by skin segments. Average of 6 skin segments for the change from baseline and % change from baseline in melanin density at each visit.

The following endpoints will be analysed using either ANCOVA or ANOVA model. The ANCOVA model will include the treatment group, randomization strata as fixed factors together with continuous covariate terms for the corresponding baseline values except for the below total

time endpoints.

- Change from baseline for in-clinic sunlight exposure time (minutes) to the first prodromal symptoms or end of test, whichever comes first.
- Total time (hours) during the 26-week double-blind treatment period in duration of sunlight exposure between 1 hour post sunrise and 1 hour pre-sunset without prodromal symptoms.
- Total time (hours) during the 26-week double-blind treatment period in duration of sunlight exposure between 1 hour post sunrise and 1 hour pre-sunset without prodromal symptom with the severity of greater than 0 on 11-point Likert scale and without phototoxic reactions (pain-free time hours).
- Change from baseline in average daily duration of sunlight exposure regardless of time of day without prodromal symptoms assessed at Week 26.

The following endpoints will be summarized using descriptive statistics and Wilcoxon's rank sum test.

- Total number of days subject is exposed to sunlight for any duration without prodromal symptoms during 26-week double-blind treatment period.

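### SAP 7.2.4 lets melanin-density values be ruled invalid after unblinding, with no blind decider and no all-values analysis, so two exploratory results could be biased

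*SAP*

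**What the plan says.** SAP 7.2.4 puts pharmacokinetic (PK) and MD data under one rule. Handling is to be confirmed at the blinded data review, and data judged invalid "will be flagged in the listing and will be excluded from the calculation of summary statistics". The section then says that "some issues may only be discovered after PK data and MD data are unblinded". For that case it continues: "Should new issues be identified post unblinding, and new data handling rules would have to be applied". What it then calls for is written justification: "a separate PK data and MD data handling document will be produced to provide detailed rationale and decision making". Data may be declared invalid after unblinding where there is clear evidence of PK or MD handling errors, or of other factors, that produced erroneous data. A full explanation is required.

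Protocol 11.6 notes that MD values could reveal treatment and says that "adequate measures will be taken to protect the spectrophotometry data from disclosure to the sponsor and the study team until the end of the study". Dedicated site staff and a dedicated data management team, both described as unblinded, measure and process the data.

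MD is used in two comparisons. In SAP 8.2.3 the six-segment average and its change from baseline "will be analysed using MMRM model similar to the analyses for the primary endpoint". SAP 8.2.1 says that the primary model gives each dose against placebo with confidence intervals and p-values. SAP 8.2.1 also lists average baseline MD, at or above versus below the median, among the subgroups for the primary endpoint.

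**The concern.** A rule that removes data should be fixed, or applied, without knowledge of treatment arm. SAP 7.2.4 guarantees neither for MD. Its three gaps are the open-ended reference to other factors, the absence of any requirement that the deciders be blind to arm, and the absence of a parallel analysis with every value kept.

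Sharing a rule with PK hides the difference between the two. Under Protocol 11.6, PK samples are analysed only for subjects on active drug, so a late PK exclusion cannot distort a drug-placebo contrast. Under Protocol 10.7.2.3, MD is measured in all subjects on the same six skin segments. A late MD exclusion can therefore enter a drug-placebo estimate directly, and a reader of the report would have no way to see whether the pigmentation result depends on it.

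**Working it through.** The plan gives no figure for MD variability, expected exclusions or MD power, so there is no stated figure to reproduce. The check is a reading of the text followed by an illustration.

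**Reading the text**

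| Question | What the documents give |
|---|---|
| May rules change after unblinding? | Yes (SAP 7.2.4) |
| Evidence needed? | Clear evidence of an error, or other factors, leading to erroneous data |
| Documentation? | Separate handling document with rationale |
| Must deciders be blind to arm? | Not stated |
| Objective MD invalidity criteria? | None in the SAP |
| Analysis keeping all values? | None planned |
| Do invalid values also leave the MMRM and the median split? | Not stated; only the listing and summary statistics are named |
| Does unblinding mean release of treatment codes? | Not separated from release of the MD values, but Protocol 11.6 concedes that the values can reveal the arm |
| Is MD in the alpha-controlled sequence? | No; H1 to H12 do not include it |

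**Worst-case illustration for the MMRM**

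Inputs: about 61 subjects per arm (Protocol 8.1: 184 randomized, 184/3 = 61.3). Assumptions: no true effect, normal data, one visit, a t test, and the k lowest values removed from one active arm.

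- Standard error of the difference: sqrt(2/61) = 0.181 SD.
- Mean shift for k = 3, large-sample approximation for trimming 5%: phi(1.645)/0.95 = 0.109 SD. By simulation with 3 of 61 removed it is 0.103 SD.
- Shift in standard errors: 0.103/0.181 = 0.57.

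Simulated false-positive rates:

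| Values dropped | Favouring active (nominal 2.5%) | Two-sided (nominal 5%) |
|---|---|---|
| 1 | about 4% | about 6% |
| 2 | about 6.5% | about 8% |
| 3 | about 9% | about 10% |
| 5 | about 16% | about 16% |

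**Baseline median split**

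Assume all 184 subjects have a baseline value and no ties. The median lies between ranks 92 and 93.

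- Drop the 3 lowest: 181 remain, and the median is their 91st value, original rank 91 + 3 = 94. Rank 93 moves from the upper to the lower group, so one subject changes.
- Drop the 3 highest: the median is rank 91. Ranks 91 and 92 move from the lower to the upper group, so two subjects change.

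**The case against.** The strongest reply is that SAP 7.2.4 sets a real threshold. A reader might infer that a document written afterwards is all that is needed, or that outliers may be dropped at will. The text supports neither: it asks for clear evidence of an error that led to erroneous data, and it nowhere makes extremeness a ground for exclusion. The simulated rates describe outcome-based trimming, which the clause does not authorise. The planned model also uses a six-segment average over several visits, so one faulty reading need not remove a subject. This part of the reply stands, and it limits the figures to an upper-bound illustration.

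It is also fair to say that late discovery of errors is to be expected. Protocol 11.6 keeps MD values from the sponsor and study team, so some instrument faults may surface only when the values are released. Late cleaning cannot be called unnecessary for MD.

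Finally, Protocol 11.6 places MD handling in the data management plan and related procedures, and SAP 7 refers to data review minutes. None of these is available here, so pre-set MD validity checks may exist elsewhere.

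What the reply leaves untouched is that a threshold and a rationale make a decision traceable but not blind. The reference to other factors weakens the threshold, and the SAP itself promises no result with all values retained.

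**Conclusion.** The point holds as a gap in safeguards for exploratory analyses. Exclusions made with the arm known could bias the MD comparison between arms in either direction. How far the text allows this depends on two things it leaves open: whether invalid values leave the MMRM and the median split, and whether the deciders hold treatment codes.

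A reader might infer that the primary result or the trial's type I error is at risk. The documents do not support that. MD lies outside H1 to H12, and Protocol 14.3.2.1 calls the subgroup analysis exploratory and says that it will not alter the terms of the primary model. The rate of about 10% for three dropped values is a worst case under the stated assumptions. It is neither a forecast nor an error rate that the plan claims to control. The effect on the subgroup cut is small: one or two subjects of 184 in the example.

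**What to change.** Amend SAP 7.2.4 as follows.

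1. Separate MD from PK.
2. Before treatment codes are released, list objective grounds for calling an MD value invalid (instrument, calibration or procedure errors), in place of the open reference to other factors.
3. Have any later invalidity decision made by staff without access to treatment codes. The existing MD data management team could do this from listings with scrambled subject identifiers, once it is confirmed that the team does not hold the codes. Because MD values can themselves suggest the arm, scrambling reduces the risk but does not remove it, so item 2 is the stronger protection.
4. State whether invalid values also leave the MMRM and the baseline median split.
5. Report the MD MMRM and the baseline-MD subgroup with and without any values excluded after unblinding.

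A proven instrument error need not be kept in the main result; showing both versions is enough. The cost is SAP wording, one extra listing review and a small amount of extra analysis. If the codes have already been released when this is taken up, items 3 to 5 can still be applied.

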7.3 Analysis Visit Definitions

(1) eDiary data excluding in-clinic sunlight exposure test

The subjects will, in their diaries, record the sunlight exposure periods (start/end time), prodromal symptom periods, and pain periods. The subjects' sunlight exposure start and end times will be compared with their state capital cities sunrise and sunset times.

The analysis windows are defined in the table below. The nominal day for each week relative to the first dose day will be used. Day 1 is the first dose day.

Table 2 Analysis Visit Window for diary data

Analysis Visit	Nominal day	Analysis Visit Window for DBT analysis
Baseline*	Day 1	Day -14 to -1
Week 2	Day 15	Day 1 to 14
Week 4	Day 29	Day 15 to 28
Week 6	Day 43	Day 29 to 42
Week 8	Day 57	Day 43 to 56
Week 10	Day 71	Day 57 to 70
Week 12	Day 85	Day 71 to 84
Week 14	Day 99	Day 85 to 98
Week 16	Day 113	Day 99 to 112
Week 18	Day 127	Day 113 to 126
Week 20	Day 141	Day 127 to 140
Week 22	Day 155	Day 141 to 154
Week 24	Day 169	Day 155 to 168
Week 26 (DBT EOT)	Day 183	Day 169 to 182
Week 26 (DBE Baseline)	Day 183	Day 169 to 182
Week 28	Day 197	Day 183 to 196
Week 32	Day 225	Day 211 to 224
Week 39	Day 274	Day 260 to 273
Week 52 (DBE EOT)	Day 365	Day 351 to 364
EOT for DBT	Day 182 or discontinued during DBT	14 days before EOT for DBT
EOT for DBE	Day 365 or discontinued during DBE	14 days before EOT for DBE
Follow-up until Week 32 (DBT EOS)	6 weeks after EOT for DBT	the latest 1 to 14 days before Follow-up date not overlapping with treatment duration in DBT period
Follow-up until Week 58 (DBE EOS)	6 weeks after EOT for DBE	the latest 1 to 14 days before Follow-up date not overlapping with treatment duration in DBE period

During 26 weeks (DBT)	1 to 182	Day 1 to EOT for DBT period
During 26 weeks (DBE)	183 to 364	DBE Baseline to EOT for DBE period

* If subjects have at least 1 day between Day -1 and Day -14, the baseline value will be calculated from the data between Day -1 and Day -14. If subjects have no data of sunlight exposure between Day -1 and Day -14, then the Analysis Visit window will be expanded to Day -28 and the baseline value will be calculated from the data between Day -1 and Day -28.

(2) Non-diary data including in-clinic sunlight exposure test

Table 3 Analysis Visit Window for non-diary efficacy data

Analysis Visit	Nominal day	Analysis Visit Window
Baseline	First dose day	NA
Week 4	Day 29	Day 16 to 64
Week 12	Day 85	Day 72 to 119
Week 26 (DBT EOT)	Day 183	Day 134 to 202
Week 26 (DBE Baseline)	Day 183	Day 134 to 202
Week 39	Day 274	Day 250 to 320
Week 52 (DBE EOT)	Day 365	Day 321 to 396
Follow-up until Week 32 (DBT EOS)	6 weeks after EOT for DBT	NA
Follow-up until Week 58 (DBE EOS)	6 weeks after EOT for DBE	NA

(3) Safety data

Table 4 Analysis Visit Window for safety data

Analysis Visit	Nominal day	Analysis Visit Window
Screening*	Day -42*	-
Baseline*	First dose day*	NA*
Week 2	Day 15	Day 2 to 22
Week 4	Day 29	Day 23 to 42
Week 8	Day 57	Day 43 to 71
Week 12	Day 85	Day 72 to 119
Week 16 (Only for Norway site)	Day 113	-
Week 18(Only for Japan and Canada site)	Day 127	-
Week 20 (Only for Norway site)	Day 141	-
Week 26 (DBT EOT)	Day 183	Day 134 to 190

Week 26 (DBE Baseline)	Day 183	Day 134 to 190
Week 28	Day 197	Day 191 to 211
Week 30 (Only for Germany site)	Day 211	-
Week 32	Day 225	Day 212 to 249
Week 36 (Only for Norway, Germany and Canada site)	Day 253	-
Week 39	Day 274	Day 250 to 320
Week 43 (Only for Norway site)	Day 302	-
Week 47 (Only for Norway site)	Day 330	-
Week 52 (DBE EOT)	Day 365	Day 321 to 396
EOT for DBT (LOCF)	Day 182 or discontinued during DBT	The latest visit during DBT period
EOT for DBE (LOCF)	Day 365 or discontinued during DBE	The latest visit during DBE period
Follow-up until Week 32 (DBT EOS)	6 weeks after EOT for DBT	NA
Follow-up until Week 58 (DBE EOS)	6 weeks after EOT for DBE	NA

* For liver function markers (ALT, AST, GGT, ALP, direct and total bilirubin), the mean value of two numerical values at screening visit and at randomization visit (the first dose day) will be treated as a baseline value.

The date of the first dose of study drug is defined as Day 1.

Unless otherwise specified, baseline will be the last observed value of the parameter of interest prior to the first intake of study drug (for DBT) or will be the available value of parameter of Week 26 (for DBE).

For other visits, if there are multiple data in a window, the closest data to nominal day will be used. If the distance to the nominal day is the same, the data of later date will be used.

According to country specific protocol for Japan, Norway, Germany and Canada, liver function markers (ALT, AST, GGT, ALP, direct and total bilirubin) will be measured at each country specific visit in each country.

